6.2 Dose Limiting Toxicities

Definitions of dose-limiting toxicity:

Toxicity will be evaluated according to CTCAE version 4.0. DLT will be defined as any of the following talimogene laherparepvec-related toxicity or related to the combination of talimogene laherparepvec and radiation therapy during treatment and through week 8:

- Grade 3 or greater immune-mediated adverse events
- Grade 3 or greater allergic reactions.
- Any grade plasmacytoma
- Any other unexpected grade 3 or greater hematologic or non-hematologic toxicity, with the exceptions of:
 - Any grade of alopecia.
 - Expected radiation related skin toxicity of any grade.
 - Grade 3 arthralgia or myalgia.
 - Brief (< 1 week) grade 3 fatigue.
 - Grade 3 fever.
 - Grade 3 diarrhea or vomiting responding to supportive care.

Of note, unless an alternative etiology has been identified, signs and symptoms of any disease process described above as a DLT should be considered immune-mediated.

If unexpected DLT occurs, talimogene laherparepvec administration should be delayed until the DLT has resolved to at least CTCAE version 4.0 grade 1. If dosing is delayed by more than 4 weeks due to the occurrence of unexpected adverse event that is considered related to talimogene laherparepvec, then the subject should be taken off treatment.

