3. OBJECTIVES

| Primary Objectives | Corresponding Primary Endpoint |
|---|--------------------------------|
| Phase 1b: To determine the safety and tolerability of neoadjuvant talimogene laherparepvec in combination with preoperative EBRT as assessed by incidence of dose-limiting toxicities (DLT) in subjects with locally advanced high grade soft tissue | Incidence of DLTs |

| | |
|--|---|
| sarcomas. | |
| Phase 2: To estimate the efficacy of neoadjuvant talimogene laherparepvec and radiotherapy as assessed by the pathological complete response rates (pCR) in subjects with histologically confirmed diagnosis of locally advanced STS that is unresectable with clear wide margins, for which preoperative radiotherapy is considered appropriate. | pCR rate - the proportion of subjects with pathologic tumor necrosis $\geq 90\%$ |
| Secondary Objectives Further assess the safety of talimogene laherparepvec given concurrently with preoperative external beam radiation in sarcoma patients. To estimate: 
• Overall response rate (ORR)• Time to progression (TTP)• Overall survival (OS) | Corresponding Secondary Endpoint Type, incidence, severity, and relatedness of AEs ORR – The proportion of subjects with a complete or partial response. TTP - Time from first day of study treatment to first documented disease progression Overall survival – Time from first day of study treatment to death due to any cause. |

For this study, pCR will be defined as $\geq 90\%$ tumor necrosis following concurrent radiation therapy and talimogene laherparepvec.

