Talimogene laherparepvec will be dosed at an initial dose of up to 4.0 mL of 10^6 PFU/mL on day 1 of week 1, followed by the target dose of up to 8.0 mL of 10^8 PFU/mL (Dose 0) three weeks later on day 1 of week 4, and dosed weekly until surgery. Initially 3 patients will be entered at the Dose 0 (following initial dose of up to 4.0 mL of 10^6 PFU/mL on day 1 of week 1) for talimogene laherparepvec and be monitored at this weekly dose through 4 injections, when safety issues will be addressed. Data from safety analysis will be reviewed with Amgen Medical and Safety team. If none or one of the 3 patients shows a DLT, three more patients will be entered into the study at this dose and be monitored at this weekly dose through 4 injections. If none or one of these 6 patients shows a DLT, this is the dose that will be used for the phase II relative efficacy assessment. Otherwise, talimogene laherparepvec dose will be deescalated and dose -1 will be explored as outlined below in Table 1. For this protocol DLT will be defined as an attributed adverse event (definite, probable or possible) that meets the criteria in Section 6.2.

Phase 2:

The phase 2 part of the study will provide an estimate of the relative treatment effect of talimogene laherparepvec in combination with preoperative EBRT in subjects with histologically confirmed diagnosis of locally advanced STS that is unresectable with clear wide margins, for which preoperative radiotherapy is considered appropriate, as measured by pathological response rates. Twenty- eight (28) patients will be enrolled into the phase 2 portion of this protocol.

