6. DOSING DELAYS/DOSE MODIFICATIONS

6.1 Dose Delays

If talimogene laherparepvec treatment was delayed due to adverse events or other reasons by > 1 week, that dose will be deemed to have been missed and the subject will proceed to the next scheduled treatment visit.

If dose-limiting toxicities occur, talimogene laherparepvec administration should be delayed until the DLT has resolved to at least CTCAE version 4.0 Grade 1 (see Appendix E). Dosing of talimogene laherparepvec could also be delayed for active herpetic cutaneous or mucosal lesions, herpes labialis, or active dermatoses in the region of the injected tumors. Talimogene laherparepvec should be discontinued for subjects with evidence of systemic herpetic infection, herpetic keratitis, encephalitis, or evidence of other disseminated herpetic infection or any herpetic infection requiring treatment with acyclovir or a similar agent.

If talimogene laherparepvec dosing is delayed by more than 4 weeks due to the occurrence of DLT or adverse events that are related to talimogene laherparepvec, then treatment should be discontinued. If talimogene laherparepvec dosing is delayed by more than 4 weeks for reasons other than treatment-related toxicity, the case must be reviewed by the sponsor of the investigator sponsor study (ISS) to determine if the subject can resume talimogene laherparepvec therapy.

If the subject requires corticosteroid dosing of > 10 mg prednisone daily (or equivalent) and/or other immunosuppressive medication for related toxicities, talimogene laherparepvec dosing must be held until the corticosteroid dose has decreased to < 10 mg prednisone daily (or equivalent) and the administration of the other immunosuppressive medication has discontinued.

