- a. Assessments will occur on Day 1 (+/- 3 days) of the week number.
- b. Blood pressure, resting pulse, respiration rate, and temperature.
- c. All serious adverse events (SAEs) will be reported within 24 hours of the discovery of the event.
- d. May be monitored more frequently if indicated.
- e. Tumor assessment will be documented per RECIST.
- f. CT chest, abdomen, and pelvis at screening (up to 28 days prior to initiation of treatment) and Week 12 (End of treatment)
- g. Primary tumor (MRI/CT) at screening (up to 28 days prior to initiation of treatment)) and on Day 1 week 12 (\pm 2 weeks). Simulation scans done for radiation planning are acceptable
- h. Follow up per standard of care (approximately every 12-16 weeks), at the discretion of the treating physician and as per NCCN guidelines. Data for survival status and disease recurrence only will be collected through chart review.
- i. Correlative labs for serologic and inflammatory response; 1 Marble Red top and 1 Pink top . See Section 9 (+/- 7 days).
- j. Talimogene laherparepvec will be given weeks 1 through 12 (+/- 2 weeks) when surgery is expected to be performed. The injections must be given the same day of the week +/- 3 days.
- k. Optional tumor biopsy can be done anytime before week 1 dosing

10.2 Screening Procedures:

- Procedures to be completed within 28 days of enrollment/randomization and prior to first treatment (unless otherwise noted).
 - Informed Consent
 - Review of eligibility criteria
 - Recording of medical history and concomitant medications
 - Physical Exam (including weight)
 - ECG
 - Vital Signs (Blood pressure, resting pulse, respiratory rate, temp.)
 - Radiographic imaging (Chest, abdomen, and pelvis and all other sites of disease)
 - Imaging of primary tumor site
- Laboratory Assessments
 - Within 28 days of enrollment and prior to first treatment.
 - HIV test: Required if clinically indicated
 - Hepatitis B and/or C tests: Required if clinically indicated
 - \leq 10 days of enrollment
 - Hematology panel (with 5 part differential). 3 part differential if 5 part unable to be performed.
 - Chemistry panel
 - Coagulation panel
 - Thyroid function tests
 - \leq 3 days of enrollment
 - Serum or urine pregnancy test for females of childbearing potential

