12. STATISTICAL CONSIDERATIONS

12.1 Study Design/Endpoints

Phase Ib

| Number of Patients with DLT at a Given Talimogene Laherparepvec Dose | Decision Rule |
|--|---|
| ≥ 2 | Dose level will be declared toxic. If this is the lowest dose level, stop the study due to excessive toxicity; otherwise enter three additional patients at the next lowest dose level. |
| ≤ 1 out of 3 | Enter three more patients at this dose level. |
| ≤ 1 out of 6 | This is the recommended Phase II dose. |

Up to 6 patients will be treated at each dose level. The recommended Phase II dose will be defined as the highest dose level for which at most 1 out of 6 patients experience a DLT.

Phase II

The primary objective of the Phase II portion of this study is to evaluate the preliminary evidence of anti-tumor activity of talimogene laherparepvec in combination with external beam radiation therapy. The primary endpoint of interest is pathologic complete response (pCR) rate defined as the proportion of subjects with pathologic tumor necrosis of $\geq 90\%$. Estimates of historic pCR based on tumor necrosis $\geq 90\%$ for the treatment of soft tissue sarcomas with external beam radiation therapy are not available in the current literature. However, a pCR rate of 30% would be considered unacceptable for the proposed combination treatment whereas a pCR of 55% or more is considered clinically important. Sample size requirements are based on an optimal Simon two-stage design with 80% power and a significance level of 5%. Nine (9) patients will

be enrolled in the first stage, and the study will be terminated if 3 or fewer respond. Otherwise, an additional 26 patients will be enrolled in the second stage. If 15 or more of the 34 total patients respond, the treatment will be deemed worthy of further investigation. This design has an expected sample size of 16.0 and a 0.73 probability of early termination.

Data Analysis and Reporting

The number and severity of all adverse events will be summarized by simple descriptive statistics. pCR and ORR (CR+PR) rate point estimates and 95% exact confidence intervals will be reported. For TTP (time from first day of study treatment to first documented disease progression) and OS (time from first day of study treatment to death due to any cause), survival curves using the Kaplan-Meier method will be constructed. Estimates along with 95% confidence intervals will be reported.

REFERENCES

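### The week 8 end of the DLT period (Section 6.2) does not fit the cohort review in 5.1, the Dose -1 schedule or the toxicity hold rules in 6.1 to 6.3

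*Combined protocol and SAP*

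**What the plan says.** Section 3 makes "Incidence of DLTs" the phase 1b primary endpoint. Section 5.1 defines a DLT by reference to Section 6.2, which counts listed toxicities related to the virus, or "related to the combination of talimogene laherparepvec and radiation therapy during treatment and through week 8".

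The calendar goes further. Footnote j of Section 10.1 reads: "Talimogene laherparepvec will be given weeks 1 through 12 (+/- 2 weeks) when surgery is expected to be performed".

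In Section 5.1, target dosing starts on day 1 of week 4. The first three patients are to "be monitored at this weekly dose through 4 injections, when safety issues will be addressed", and the next three are monitored for the same number of injections. Then: "If none or one of these 6 patients shows a DLT, this is the dose that will be used for the phase II" part. Section 12.1 selects "the highest dose level for which at most 1 out of 6 patients experience a DLT" and gives no period of its own.

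The same term governs patient management. Section 6.1: "If dose-limiting toxicities occur, talimogene laherparepvec administration should be delayed until the DLT has resolved to at least CTCAE version 4.0 Grade 1". Section 6.2: "If unexpected DLT occurs, talimogene laherparepvec administration should be delayed until the DLT has resolved to at least CTCAE version 4.0 grade 1". Section 6.3 moves a patient to every-2-week dosing after two consecutive doses are missed because of a DLT.

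**The concern.** One dated definition serves two purposes: counting events for the 1-in-6 dose rule, and triggering what must be done for the individual patient. A short, fixed period suits the first. The second should last as long as injections do.

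Week 8 falls inside treatment, so each part of the plan that relies on the definition has to be checked against that date. Three do not match:

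- **Cohort review.** The 5.1 review is set by injection count and can come before the 6.2 period closes.
- **Dose -1.** A period fixed in calendar weeks covers fewer injections on the slower schedule.
- **Hold and step-down.** A qualifying toxicity in week 10 is literally not a DLT, so these rules do not reach it.

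At stake are the dose that all phase 2 patients receive and the consistency of toxicity management over the last four injections. The dose of 8 mL is twice the volume tested in the earlier sarcoma trial.

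**Working it through.** The plan states no DLT rate, pass probability or error rate for phase 1b, so there is no figure of its own to reproduce.

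**Timing**, from 5.1, 5.2.1 and footnote j of 10.1:

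- Dose 0, weekly from week 4: the fourth target-dose injection is on day 1 of week 7, the fifth in week 8 and the ninth in week 12. The 6.2 period therefore contains five of nine, and 5.1 calls for review after four.
- From day 1 of week 7 to the end of week 8 is about 2 weeks. A toxicity in that interval, including one after the week 8 injection, is a DLT under 6.2 but can arise after the cohort decision. The available text of 5.1 does not say that the decision waits, or what a DLT arising afterwards does to it.
- Dose -1, every 2 weeks from week 4: injections fall in weeks 4, 6, 8, 10 and 12. Three lie within week 8. The fourth falls in week 10, outside the period.
- Weeks 9 to 12 contain four weekly injections at Dose 0, all after the period closes.

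**Effect on dose selection.** Assume equal DLT risk at each of nine target-dose injections and a full-course risk P. After k injections the risk is p = 1 − (1 − P)^(k/9). The dose passes with at most 1 DLT in 6, so the pass probability is (1 − p)^6 + 6p(1 − p)^5. At most 1 in 6 already implies at most 1 in the first 3. P is an assumption, shown as a range.

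| P | p, k = 4 | pass, k = 4 | p, k = 5 | pass, k = 5 | difference |
|---|---|---|---|---|---|
| 0.10 | 0.0457 | 0.9722 | 0.0569 | 0.9584 | 0.0138 |
| 0.20 | 0.0944 | 0.8966 | 0.1166 | 0.8517 | 0.0449 |
| 0.33 | 0.1630 | 0.7455 | 0.1995 | 0.6567 | 0.0888 |

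Deciding at the close of the 6.2 period instead of at the fourth injection lowers the chance of passing by about 1, 4 and 9 points.

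Footnote j allows 2 weeks either way. With 7 injections in all, the difference at P = 0.33 is 0.644 − 0.537 = 0.107. With 11 it is 0.810 − 0.737 = 0.073.

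**Which rules still apply in weeks 9 to 12.** Several are not tied to the term DLT:

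- 5.2.1 allows delay or de-escalation for severe events.
- 5.4 ends treatment for unacceptable events.
- 5.6 requires stopping for related Grade 3 or higher toxicity that the investigator judges to need more than 4 weeks' delay or discontinuation.
- 6.1 stops treatment after more than 4 weeks' delay for related events, and requires a hold while prednisone exceeds 10 mg daily for related toxicity.

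None of these requires a hold until Grade 1 merely because a 6.2 criterion has been met.

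**The case against.** The strongest reply is that 6.2 is clear enough. It gives one end date. Adverse events are collected from consent, so the reference to treatment can simply mark where the DLT period starts. The review after four weekly injections falls close to week 8. This stands, and it is why the period is taken here as first injection through week 8.

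A reader might nevertheless infer that the period equally well covers all of treatment, so that the events counted by the 1-in-6 rule are undetermined. Comparing a week 8 close with follow-up of all six patients to week 12, under the same assumption, gives opposite decisions in 7%, 20% and 30% of trials at P = 0.10, 0.20 and 0.33. The documents do not support that comparison, because 5.1 decides after four injections and contains no rule to follow all six for the full course. If only the first three are followed throughout and the last three to week 8 (risk p at k = 5), the pass probability is (1 − P)^3(1 − p)^3 + 3P(1 − P)^2(1 − p)^3 + 3p(1 − p)^2(1 − P)^3 = 0.926, 0.757 and 0.498. Against 0.958, 0.852 and 0.657 the gap is 3, 9 and 16 points.

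The higher risks also lack support. The earlier sarcoma trial reported no DLTs at 4 mL. If that means 0 in all 30 enrolled, the one-sided 95% upper bound is 1 − 0.05^(1/30) = 9.5%. Seventeen head-and-neck patients given the virus with chemoradiotherapy had none. This stands too, although 8 mL is untested.

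A reader might also see a conflict over plasmacytoma, which is a DLT (hence a hold) in 6.2 but requires permanent discontinuation in 5.6. The specific rule in 5.6 settles it.

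Finally, the timeline figures are not available, and the table cited in 5.1 does not appear under that label. They may say more about when decisions are made.

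**Conclusion.** The concern holds as three mismatches around a week 8 close, not as an undefined endpoint: a review that can precede the end of the period, a period that gives Dose -1 three target-dose injections, and required hold and step-down rules that literally lapse for weeks 9 to 12.

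For dose selection the first mismatch is worth about 1, 4 or 9 points of pass probability at assumed full-course risks of 10%, 20% or 33%. It is smaller if DLTs come early or the risk is below 10%. These figures rest on equal risk per injection, independent patients and nine target-dose injections; the documents give no DLT rate at 8 mL. The hold-rule mismatch carries no number. Investigator discretion and the steroid rule limit its consequences but do not remove it. Phase 2 sample size and error rates are unaffected. This is a worthwhile clarification, not a flaw that undermines the trial.

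**What to change.** 1. **Section 6.2:** for the dose decision, define the DLT period as *from the first injection to the end of week 8*, and state the matching end for Dose -1. If four target-dose injections are wanted there, with the same 2 weeks or so afterwards, that is the end of week 11. If three are accepted, say so.
2. **Section 5.1:** make each cohort decision only after every patient in the cohort has completed that period.
3. **Sections 6.1 to 6.3:** apply the hold and step-down to any toxicity meeting a 6.2 criterion at any time during treatment, whether or not it counts for the dose decision. The discontinuation rules in 5.6 stay as they are.

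These are wording changes for one amendment. Waiting from the fourth injection to the end of week 8 adds at most about 2 weeks per cohort of three, so about 4 weeks for two cohorts in sequence at Dose 0.

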The target volume for postoperative radiotherapy will be the residual tumor bed as defined by the surgical and pathological findings.

External Beam Radiotherapy

Postoperative external beam boost dose is 16 Gy in 8 fractions (once a day).

Brachytherapy

High-dose-rate (HDR) brachytherapy as a boost to the positive tumor margin can be used as an alternate to external beam radiotherapy. Brachytherapy catheters are placed at an interval of 0.5 -1.0 cm on the residual tumor bed (positive margin) plus a margin of 1 cm during surgery. Skin surface dose should be kept below 50% of the prescription dose unless positive margins occur in cutaneous or subcutaneous tissues. It is not necessary to include the entire surgical bed, drain sites and wound.

Brachytherapy should not start until day 5 after the surgery (day 0) and must be completed within 2 weeks following surgery.

For HDR brachytherapy, 4 fractions of 3.4 Gy are delivered b.i.d, with an interval of at least 6 hours between fractions.

Radiation Therapy Adverse Events

Acute: Wound complications of any grade are expected to develop in about one third of patients. Other common radiation adverse events include: fatigue, regional alopecia, diarrhea, skin erythema and desquamation within the treatment fields, and reduction in blood counts.

Long-term: Common long-term treatment adverse events include: lymphedema of the extremity receiving radiation and surgery, subcutaneous fibrosis, and joint stiffness. Much less common radiation adverse events include bowel injury, osteoradiation necrosis, and bony fracture in the radiation field. There also is a risk of secondary malignancy occurring in the irradiated field.

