5.6 Criteria for Removal from Study

Talimogene laherparepvec is to be permanently discontinued for subjects meeting any of the following criteria:

- The subject, for any reason, requires treatment with another anticancer therapeutic agent for treatment of the study disease (other than the exceptions noted in protocol, if applicable). In this case, discontinuation from the treatment occurs immediately upon introduction of the new agent.
- Clinical relevant disease progression as defined in the study protocol.
- Immune-mediated adverse events have been observed in subjects receiving talimogene laherparepvec. These have included pauci-immune glomerulonephritis, vasculitis, and pneumonitis; however, immune-mediated adverse events can potentially involve any organ system. Permanently discontinue talimogene laherparepvec if dosing is delayed by more than 4 weeks due to a Grade 2 or greater immune-mediated adverse event (with the exception of vitiligo), allergic reactions, or urticaria attributed to talimogene laherparepvec.
- Plasmacytoma has been observed with the administration of talimogene laherparepvec. Permanently discontinue talimogene laherparepvec if development of a plasmacytoma is observed.

- Any talimogene laherparepvec-related non-hematologic or hematologic toxicities Grade 3 or greater that, in the opinion of the investigator, would require a dose delay of greater than 4 weeks or discontinuation of therapy.
- A female subject becomes pregnant or fails to use 2 highly effective methods of contraception (for those subjects who are able to conceive).
- A female subject breast feeds while on study treatment.
- A male subject fails to use a highly effective method of contraception as described in Section 7.5.
- Intercurrent medical illness that, in the judgment of the investigator, would make continued treatment with talimogene laherparepvec dangerous for the subject.

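### Section 6.2 has no criterion that makes permanent discontinuation a DLT, so an exempted drug-related Grade 3 event can end treatment without entering the Phase Ib count that selects the dose

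*Combined protocol and SAP*

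**What the plan says.** Section 5.1 (Phase 1b) ties the dose-finding endpoint to one place: "For this protocol DLT will be defined as an attributed adverse event (definite, probable or possible) that meets the criteria in Section 6.2". Section 12.1 then recommends "the highest dose level for which at most 1 out of 6 patients experience a DLT". Two or more DLTs make the level toxic. The next step is dosing every 2 weeks or, at the lowest level, stopping the study.

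Section 6.2 considers toxicity related to the drug, or to the drug with radiation, through week 8. It has four criteria: Grade 3 or greater immune-mediated events, Grade 3 or greater allergic reactions, plasmacytoma of any grade, and "Any other unexpected grade 3 or greater hematologic or non-hematologic toxicity". Six exceptions hang on the fourth criterion. Among them are Grade 3 arthralgia or myalgia, Grade 3 fever, and "Expected radiation related skin toxicity of any grade". None of the four criteria mentions discontinuation, missed doses or prolonged delay.

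Two other sections govern stopping the drug. Section 5.6 requires permanent discontinuation for "Any talimogene laherparepvec-related non-hematologic or hematologic toxicities Grade 3 or greater that, in the opinion of the investigator, would require a dose delay" of more than 4 weeks, or discontinuation. Section 6.1 deals with delays of more than 4 weeks "due to the occurrence of DLT or adverse events that are related to talimogene laherparepvec, then treatment should be discontinued".

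**The concern.** A patient who must stop the drug permanently because of related Grade 3 toxicity is direct evidence against tolerability. The Phase Ib endpoint is the incidence of DLTs, and that count alone decides between weekly dosing, dosing every 2 weeks, and stopping. If such a patient can be recorded as DLT-free, the count can understate toxicity in exactly the cases that matter. In the extreme, two of six patients could be taken off the drug under Section 5.6 and the dose would still pass with no DLTs.

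The question is not settled by earlier sarcoma experience. The trial described in Section 1.2.1 saw no DLTs at 4 mL, whereas this one gives up to 8 mL at each weekly injection.

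**Working it through.** **Step 1. Which events can meet Section 5.6 and not Section 6.2?**

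- *Fever, arthralgia, myalgia (Grade 3).* Section 6.2 exempts these without a limit on duration or outcome. By contrast, fatigue is exempt only if it lasts less than a week, and diarrhea or vomiting only if it responds to supportive care. The exemption applies whatever *unexpected* means. Arthralgia or myalgia judged immune-mediated still counts under the first criterion, which has no exceptions. The gap is therefore Grade 3 fever, and Grade 3 arthralgia or myalgia not judged immune-mediated.
- *Radiation skin toxicity.* Section 5.2.4 lists "skin erythema and desquamation within the treatment fields" among common radiation effects, and the injected tumor lies in that field. Section 6.2 reaches events related to the combination, but Section 5.6 reaches only events related to talimogene laherparepvec. A skin reaction falls in the gap only if it is also judged talimogene-related.
- *Listed events such as Grade 3 injection-site cellulitis.* These fall in the gap only if *unexpected* has its Section 7.1 meaning and the Investigator Brochure lists the event at that severity. Section 6.2 does not cite Section 7.1, and the brochure table is not in the documents. This is a possibility only.

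**Step 2. Does other text in Sections 6.1 or 6.2 close the gap?** The last paragraph of 6.2 takes a patient off treatment after a delay of more than 4 weeks for an unexpected related event, but that is an instruction on management and not a DLT criterion. The 6.2 note on presuming an immune-mediated cause applies to processes already described there as DLTs, which exempted events are not. Section 6.1 names DLTs and other related events as alternative reasons to stop, so the protocol itself foresees stops that are not DLTs.

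**Step 3. Size.** The plan states no operating characteristics for Phase Ib, so there is no figure to reproduce. Let c be the rate of DLTs as now defined and q the rate of forced stops that are not counted, in different patients. Then

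P(pass | p) = (1 − p)^6 + 6p(1 − p)^5,

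with p = c under the present rule and p = c + q if the stops counted. Working through the two steps (at most 1 of 3, then at most 1 of 6) gives the same values.

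Both rates are assumptions. For q, 2.4% is borrowed from Section 7.3.1, where it is the proportion with serious cellulitis in the pivotal study. Neither the grade of those events nor any discontinuation is given.

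| c | q | P(pass), present rule | P(pass), stops counted |
|---|---|---|---|
| 5% | 1.2% | 0.967 | 0.951 |
| 5% | 2.4% | 0.967 | 0.933 |
| 2% | 2.4% | 0.994 | 0.974 |
| 10% | 2.4% | 0.886 | 0.836 |

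For c = 5% and q = 2.4%: 0.926^6 + 6 × 0.074 × 0.926^5 = 0.631 + 0.302 = 0.933. The two rules would disagree in about 0.967 − 0.933 = 0.034 of cohorts. With c at 2% or 10%, the difference is 0.020 or 0.050.

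At q = 2.4% alone, the chance of at least one such stop among six patients is 0.136, and of two or more, 0.008.

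**The case against.** **The exempt events may rarely end treatment.** Section 1.2.2 describes flu-like symptoms, pyrexia and myalgia among them, as self-limiting and resolving without sequelae. The one drug-related discontinuation the documents describe for a specific event is a plasmacytoma, which already counts at any grade. This stands, and it is why the expected effect is small. It does not supply the missing criterion.

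**The events are not hidden.** The affected patient stops the drug in any case. Section 5.1 says "Data from safety analysis will be reviewed with Amgen Medical and Safety team", and that review is not confined to DLTs. Under Appendix E the data and safety monitoring committee receives every serious adverse event and looks at cumulative trends. This also stands. But neither body has a numeric rule for the dose, and the stopping-rules paragraph of Appendix E provides only an accrual hold after a death during treatment.

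**The distinction may be deliberate.** Section 6.1 separates DLTs from other related events, and no statement in the protocol contradicts another. That is fair: this is a design choice that can be improved, not an error.

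**Two stronger readings are tempting.** A reader might infer that serious cellulitis certainly escapes the count. The documents do not show this: Appendix D lists cellulitis without a grade, and Section 7.1 treats an event as unexpected if it is not listed at the severity observed. A reader might also try to bound the uncounted rate from the head and neck study in Section 1.2.1, where none of 17 patients had a DLT. A zero count of DLTs cannot bound the rate of events that are, by definition, not DLTs.

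**Conclusion.** The gap is real and narrow. It is established for drug-related Grade 3 fever, and for Grade 3 arthralgia or myalgia not judged immune-mediated, when such an event meets the Section 5.6 criterion. It extends to radiation skin reactions only when they are also attributed to talimogene laherparepvec. For listed events such as Grade 3 cellulitis it is conditional on a source that is not in the documents.

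Its true size cannot be known from the documents. The fall of 0.034 in the chance that a dose passes rests on an assumed 5% DLT rate, an assumed 2.4% rate of uncounted stops, and no overlap between the two. A reader might infer that the Phase Ib result would be unreliable; these figures do not support that. This is a minor point at the low end of that grade, worth making because the correction is cheap and the volume per injection is new.

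**What to change.** Keep the Grade 3 threshold and all the exceptions, and add one bullet to Section 6.2:

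> *Any other talimogene laherparepvec-related Grade 3 or greater toxicity, expected or exempted above, with onset by week 8, that meets the Section 5.6 criterion for permanent discontinuation.*

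Record the investigator's Section 5.6 judgement at the cohort review. Section 5.6 asks whether the event would require the delay, so no one has to wait for 4 weeks to pass. Expected or exempted events that recover and allow dosing to continue still do not count. Because the bullet covers expected events, treatment-ending cases no longer depend on what *unexpected* means.

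The cost is one bullet and one recorded judgement per event, from data already collected. There are two downsides. An acceptable dose is slightly more likely to be rejected: at the illustrative rates the chance of rejection rises from 1 − 0.967 = 0.033 to 1 − 0.933 = 0.067. The count would also rest partly on investigator opinion in an open-label study, as Section 5.6 already does. The change does not reach events that start after week 8, such as healing problems after surgery at weeks 12 to 14.
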